10.4.2. Attribution Definitions

Assessment of Causality

The causal relationship to study intervention is assessed by the investigator and documented in the Medical Records.

The assessment of causality must consider the following factors:

- Temporal relationship
- Clinical characteristics of event
- Pharmacological plausibility
- Confounding risk factors:
 - Concomitant medication
 - Underlying/concurrent disease
 - Family/social history
- Challenge:
 - De-challenge: Did the reaction improve when the investigational product was withdrawn, in the absence of any other treatment?
 - Re-challenge: What happens if participant is re-challenged with investigational product?
- Other considerations: Participant characteristics and past medical history, and quality of information

The following selection must be used to assess all AEs.

Related

There is a reasonable causal relationship between study intervention administration and the AE.

Not Related

There is not a reasonable causal relationship between study intervention administration and the AE.

10.4.3. Severity Criteria

An assessment of severity grade will be made by the investigator using the general categorical descriptors outlined in the DAIDS Toxicity Grading Scale (see Section 10.9, Appendix 9: DAIDS Table).

The investigator must use clinical judgement in assessing the severity of events not directly experienced by the participant (eg, laboratory abnormalities).

10.4.4. Special Reporting Situations

Safety events of interest on a sponsor study intervention in an interventional study that may require expedited reporting or safety evaluation include, but are not limited to:

- Overdose of a sponsor study intervention
- Suspected abuse/misuse of a sponsor study intervention
- Accidental or occupational exposure to a sponsor study intervention
- Medication error, intercepted medication error, or potential medication error involving a Johnson & Johnson medicinal product (with or without patient exposure to the Johnson & Johnson medicinal product, eg, product name confusion, product label confusion, intercepted prescribing or dispensing errors)
- Exposure to a sponsor study intervention from breastfeeding
- Reporting of participant pregnancy or participant partner(s) pregnancy

Special reporting situations must be recorded in the CRF. Any special reporting situation that meets the criteria of an SAE must be recorded on the serious adverse event page of the CRF.

10.4.5. Procedures**All Adverse Events**

All AEs, regardless of seriousness, severity, or presumed relationship to study intervention, must be recorded using medical terminology in the source document and the CRF. Whenever possible, diagnoses should be given when signs and symptoms are due to a common etiology (eg, cough, runny nose, sneezing, sore throat, and head congestion should be reported as "upper respiratory infection"). Investigators must record in the CRF their opinion concerning the relationship of the adverse event to study therapy. All measures required for adverse event management must be recorded in the source document and reported according to sponsor instructions.

For all studies with an outpatient phase, including open-label studies, the participant must be provided with a "wallet (study) card" and instructed to carry this card with them for the duration of the study indicating the following:

- Study number
- Statement, in the local language(s), that the participant is participating in a clinical study
- Investigator's name and 24hour contact telephone number
- Local sponsor's name and 24-hour contact telephone number (for medical personnel only)
- Site number
- Participant number
- Any other information that is required to do an emergency breaking of the blind

Serious Adverse Events

All SAEs that have not resolved by the end of the study, or that have not resolved upon the participant's discontinuation from the study, must be followed until any of the following occurs:

- The event resolves
- The event stabilizes
- The event returns to baseline, if a baseline value/status is available
- The event can be attributed to agents other than the study intervention or to factors unrelated to study conduct
- It becomes unlikely that any additional information can be obtained (participant or health care practitioner refusal to provide additional information, lost to follow-up after demonstration of due diligence with follow-up efforts)

Any event requiring hospitalization (or prolongation of hospitalization) that occurs during participation in the study must be reported as a serious adverse event, except hospitalizations for the following:

- Hospitalizations not intended to treat an acute illness or adverse event (eg, social reasons such as pending placement in long-term care facility)
- Surgery or procedure planned before entry into the study (must be documented in the CRF). Note: Hospitalizations that were planned before the signing of the ICF, and where the underlying condition for which the hospitalization was planned has not worsened, will not be considered SAEs. Any adverse event that results in a prolongation of the originally planned hospitalization is to be reported as a new serious adverse event.

The cause of death of a participant in a study, whether or not the event is expected or associated with the study intervention, is considered a serious adverse event.

Information regarding SAEs will be transmitted to the sponsor using a serious adverse event reporting form, which must be completed and signed by a physician from the study site, and transmitted in a secure manner to the sponsor within 24 hours. The initial and follow-up reports of a serious adverse event should be made by facsimile (fax). Telephone reporting should be the exception and the reporter should be asked to complete the appropriate form(s) first.

10.4.6. Product Quality Complaint Handling

Definition

A PQC is defined as any suspicion of a product defect related to manufacturing, labeling, or packaging, ie, any dissatisfaction relative to the identity, quality, durability, reliability, or performance of a distributed product, including its labeling, drug delivery system, or package integrity. A PQC may have an impact on the safety and efficacy of the product. In addition, it includes any technical complaints, defined as any complaint that indicates a potential quality issue during manufacturing, packaging, release testing, stability monitoring, dose preparation, storage or distribution of the product or the drug delivery system.

Procedures

All initial PQCs must be reported to the sponsor by the study-site personnel within 24 hours after being made aware of the event.

A sample of the suspected product should be maintained under the correct storage conditions until a shipment request is received from the sponsor.

10.4.7. Contacting Sponsor Regarding Safety, Including Product Quality

The names (and corresponding telephone numbers) of the individuals who must be contacted regarding safety issues, PQC, or questions regarding the study are listed in the Contact Information page(s), which will be provided as a separate document.

10.5. Appendix 5: Rash Management

Table 3: Management of Rash Events by Severity Grade

	Definition	Study Intervention Action	Activities by Day^a	Referral to Dermatologist and Dermatology Activities
Grade 1 rash (with or without pruritus)^b	Erythema	Study intervention intake may be continued at the investigator's discretion	
 • Day 0: optional on-site visit for initial rash evaluation may be performed at the investigator's discretion. • Safety laboratory assessments may be performed at the investigator's discretion (recommended if visit occurs). • Digital pictures* of skin lesions may be taken at the investigator's discretion. • Determine if participant was adhering to the recommended sun-protective measures. If appropriate, provide sun protection counseling. • Day 1 and thereafter: appropriate follow-up visits at the investigator's discretion until resolution of rash. • Safety laboratory assessments and photography (digital pictures* of skin lesions) may be performed at the investigator's discretion. • * Digital pictures to be taken at the clinical site upon consent of the participant. 	Not required

Table 3: Management of Rash Events by Severity Grade

	Definition	Study Intervention Action	Activities by Day^a	Referral to Dermatologist and Dermatology Activities
Grade 2 rash (with or without pruritus)^b	Diffuse, maculopapular rash, or dry desquamation	Study intervention intake may be continued at the investigator's discretion	
 • Day 0: required on-site visit (if a visit is not possible, telephone contact with the participant should take place to collect information and give advice on the necessary measures to be taken). • Safety laboratory assessments may be performed at the investigator's discretion (recommended). • Digital pictures* of skin lesions may be taken at the investigator's discretion. Digital pictures* of skin lesions are recommended in case consultation of a dermatologist is required. Determine if participant was adhering to the recommended sun-protective measures. If appropriate, provide sun protection counseling. • Day 1 and thereafter: appropriate follow-up visits at the investigator's discretion until resolution of rash or until clinical stability is reached. • Safety laboratory assessments are required on Day 1 and are required thereafter only if the previous values were abnormal (but may be performed at the investigator's discretion). If the rash progresses to a higher grade, safety laboratory assessments of the higher grade should be followed. • Digital pictures* of skin lesions may be taken at the investigator's discretion. • * Digital pictures to be taken at the clinical site upon consent of the participant. 	
Referral to dermatologist at the discretion of the investigator^c
 
Biopsy not required, but may be performed at the dermatologist's discretion

Table 3: Management of Rash Events by Severity Grade

	Definition	Study Intervention Action	Activities by Day^a	Referral to Dermatologist and Dermatology Activities
Grade 3 rash^b	
 Vesiculation, moist desquamation, or ulceration OR Any cutaneous event with 1 of the following: 
 Elevations in ALT/AST >2×baseline value Fever >38°C or 100°F Eosinophils >1.00×10³/μL Serum sickness-like reaction 	
Must permanently discontinue JNJ-3989; no rechallenge allowed
 
NA treatment may be discontinued based on investigator judgement in consultation with the sponsor
	
 Day 0: required on-site visit. Safety laboratory assessments required to be performed. Digital pictures* of skin lesions may be taken at the investigator's discretion (recommended). Determine if participant was adhering to the recommended sun-protective measures. If appropriate, provide sun protection counseling. Day 1: required on-site visit. Safety laboratory assessments required to be performed. Digital pictures* of skin lesions may be taken at the investigator's discretion (recommended). Further visit(s): appropriate follow-up required until resolution of rash or until clinical stability is reached. Safety laboratory assessments and photography (digital pictures* of skin lesions) are recommended to be performed until the rash severity resolves to grade 2 or grade 1. * Digital pictures to be taken at the clinical site upon consent of the participant. 	
Required^c
 
Biopsy not required, but may be performed at the dermatologist's discretion.

Table 3: Management of Rash Events by Severity Grade

	Definition	Study Intervention Action	Activities by Day^a	Referral to Dermatologist and Dermatology Activities
Grade 4 rash	Exfoliative dermatitis OR Mucous membrane involvement in at least 2 distinct sites OR Erythema multiforme major OR Stevens-Johnson syndrome OR Toxic epidermal necrolysis OR Necrosis requiring surgery	Must permanently discontinue JNJ-3989; no rechallenge allowed NA treatment may be discontinued based on investigator judgement in consultation with the sponsor	
 • Day 0: required on-site visit. • Safety laboratory assessments required to be performed. • Digital pictures* of skin lesions may be taken at the investigator's discretion (recommended). • Determine if participant was adhering to the recommended sun-protective measures. If appropriate, provide sun protection counseling. • Day 1: required on-site visit. • Safety laboratory assessments required to be performed. • Digital pictures* of skin lesions may be taken at the investigator's discretion (recommended). • Further visit(s): appropriate follow-up required until resolution of rash or until clinical stability is reached. • Safety laboratory assessments and photography (digital pictures* of skin lesions) are recommended to be performed until the rash severity resolves to grade 2 or grade 1. • * Digital pictures to be taken at the clinical site upon consent of the participant. 	Required ^c Biopsy required and to be performed as soon as possible after the onset of the rash.

AE: adverse event; ALT: alanine aminotransferase; AST: aspartate aminotransferase; NA: nucleos(t)ide analog.

^a Day 0 of the rash is the first day of investigator assessment and not the first day of rash as reported by the participant. The initial visit should be conducted as soon as possible after the participant contacts the investigator to report the AE (ie, preferably on Day 0). The initial visit and subsequent visits to manage the rash may require unscheduled visit(s).

[figure not shown]
^b The participant should be advised to contact the investigator immediately if there is any worsening of the rash, if any systemic signs or symptoms appear, or if mucosal involvement develops. In case the rash evolves to a higher grade than that first observed, management of the rash should follow the guidelines indicated for the higher grade.

^c If applicable, dermatologist visit should occur preferably within 24 hours after onset of rash.

Note:

- Local laboratory assessments are to be used for rash management. Relevant laboratory assessment values are to be shared with the sponsor (if applicable and local regulations allow) as per the “Instructions for Investigators for sharing of Digital Pictures and Local lab reports” and should be de-identified.
- Digital pictures that are collected, dermatological consultation reports or biopsy reports that become available, should be de-identified and provided to the sponsor.

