Amendment 5 (27 March 2024)**Overall Rationale for the Amendment:**

As described in Amendment 4 dated 7 April 2023, due to the strategic decision taken by the sponsor to discontinue further investment in its hepatitis B and D discovery and development programs, enrollment of new participants into the REEF-D study was not re-opened and the study was modified to continue with the enrolled participants as planned.

The overall reason for the present amendment is to facilitate an early completion of the REEF-D study by reducing the study duration for participants in Part 2 while ensuring that all participants have the possibility to receive at least 48 weeks of JNJ-73763989 (JNJ-3989) treatment and adequate follow-up. At the time of the present protocol amendment, all participants in Part 1 and Part 2 are beyond the double-blind phase. All 22 participants in Part 1 have completed the investigational study treatment. This amendment will not affect the participants in the follow-up phase in Part 1 and will only affect the participants in Part 2. In Part 2, participants either have completed the study (n = 11), entered the open-label phase following the 52 weeks of double-blind treatment (n = 17), or are in the follow-up phase (n = 2). Once the present amendment will be approved and in effect at a given study site, the next planned visit for participants in the open-label phase, but not earlier than Week 96 (Arm 1) and Week 100 (Arm 2), will be the end of treatment (EOT) visit. At this EOT visit, JNJ-3989 will not be administered and participants will continue treatment with NA until the last study visit in the follow-up phase. All participants in Part 2 will follow a reduced follow-up phase of at least 24 weeks when the present amendment becomes effective. The decision to reduce the study duration of Part 2 is due to the sponsor's strategic decision to discontinue the development of JNJ-3989 in chronic hepatitis D disease and is not triggered by any safety findings.

The changes made to the clinical protocol 73763989HPB2004 as part of Protocol Amendment 5 are listed below, including the rationale of each change and a list of all applicable sections. Changes made in previous protocol amendments are listed in Section 10.11, Appendix 11: Protocol Amendment History.

Section number and Name	Description of Change	Brief Rationale

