7. DISCONTINUATION OF STUDY INTERVENTION AND PARTICIPANT DISCONTINUATION/WITHDRAWAL

7.1. Discontinuation of Study Intervention

A participant's investigational study intervention (JNJ-3989/placebo) **must** be discontinued if any of the criteria listed below apply. In those cases, NA treatment should be continued.

- The participant withdraws consent to receive study intervention.
- The investigator believes that for safety reasons or tolerability reasons (eg, AE) it is in the best interest of the participant to discontinue study intervention.
- The participant becomes pregnant.
- The participant has a \geq grade 3 rash (see Section 10.5, Appendix 5, Rash Management) or allergic reaction (see Section 8.3.6.3).
- The participant has signs of hepatic decompensation (ie, clinical evidence of ascites, bleeding varices, or hepatic encephalopathy) or an increase in direct bilirubin $>1.5x$ ULN in combination with INR $\geq 1.5x$ ULN or albumin <3.0 g/dL. In this case treatment with JNJ-3989 should be discontinued and alternative treatment options (outside the study) should be considered in discussion with the sponsor.

- The participant has a confirmed \geq grade 3 estimated glomerular filtration rate (eGFR) abnormality and a drop from baseline of >10 mL/min/1.73 m², considered at least possibly related to JNJ-3989 that persists despite change of tenofovir disoproxil to ETV or TAF (if the patient was receiving tenofovir disoproxil). Change of NA treatment should be considered anytime, according to the prescribing information. (see Section 8.3.6.4).
- The participant has a confirmed QTcF prolongation (defined as a QTcF value of >500 ms, or an increase from baseline of >60 ms) at any given time point.
- The participant requires treatment with any of the disallowed medications listed in Section 6.7 and does not intend to discontinue treatment with the disallowed medication.
- The participant has confirmed HBV virologic breakthrough (ie, confirmed on-treatment HBV DNA increase by >1 log₁₀ IU/mL from nadir or confirmed on-treatment HBV DNA level >200 IU/mL in participants who had HBV DNA level $<$ LLOQ of the HBV DNA assay). In case of virologic breakthrough, changing the NA should be considered in consultation with the sponsor. Injection with JNJ-3989 will be stopped if the NA change does not result in a decrease in HBV DNA levels.
- The participant has ALT/AST elevations, as described in Section 8.3.6.1, Intervention-emergent ALT/AST Elevations.

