8.2.2. Vital Signs

Temperature (tympanic or oral), body weight, pulse rate, and blood pressure will be assessed.

Blood pressure and pulse rate measurements will be assessed with a completely automated device. All values will preferably be registered on a built-in recorder so that measurements are observer independent. Manual techniques will be used only if an automated device is not available.

Blood pressure and pulse rate measurements should be preceded by at least 5 minutes of rest in a quiet setting without distractions (eg, television, cell phones).

Clinically relevant abnormalities in vital signs are defined in Section 10.7, Appendix 7: Cardiovascular Safety Abnormalities.

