8.3.6.2. Rash

Participants should be informed that they should contact their doctor immediately when they notice any generalized skin reaction. This skin reaction should be evaluated in the clinic the same day (if possible) or the next day.

All rash events should be captured in the AE section of the CRF. A separate Rash page will be completed in case of a rash event.

Monitoring of the evolution of rash events will be performed as described in Table 3 in Section 10.5, Appendix 5: Rash Management.

When safety blood samples are drawn as per the rash management guidelines, these should be processed by the local laboratory. The following parameters will need to be tested: AST, ALT, sedimentation rate, complete blood cell count (including hemoglobin, hematocrit, red blood cell [RBC] count, white blood cell [WBC] count, differential count [neutrophils, lymphocytes, monocytes, eosinophils, and basophils], and platelet count), and creatinine. Relevant laboratory assessment values are to be shared with the sponsor (if applicable and local regulations allow) as per the “Instructions for Investigators for sharing of Digital Pictures and Local lab reports” and should be de-identified.

The participant may be treated symptomatically until the rash resolves. Oral antihistamines (eg, cetirizine, levocetirizine) and/or topical corticosteroids may provide symptomatic relief but effectiveness of these measures has not been established. If systemic corticosteroids exceeding 5 mg of prednisolone equivalent/day are required for treatment of rash, the study intervention needs to be permanently discontinued. If the rash is considered to be most likely due to concomitant illness or non-study drugs, standard management, including discontinuation of the likely causative agent, should be undertaken.

Injection Site Reactions

At the time points specified in the [Schedule of Activities](#) or at an unscheduled visit if needed, an evaluation of the injection site will be performed based on participant's description and/or physical examination. Evaluation will include at a minimum the time of occurrence, time of resolution and a description of the abnormality including its maximal diameter. For each ISR, information on pain, erythema, induration and pruritus should be obtained as specified in the DAIDS scale (see Section 10.9, Appendix 9: DAIDS Table).

All ISRs (including ISRs below grade 1) will need to be recorded in the special events section of the CRF.

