Fatigue or Malaise Report only 1	Symptoms causing no or minimal interference with usual social & functional activities	Symptoms causing greater than minimal interference with usual social & functional activities	Symptoms causing inability to perform usual social & functional activities	Incapacitating symptoms of fatigue or malaise causing inability to perform basic self care functions
Fever (non axillary temperatures only)	38.0°C to <38.6°C or 100.4°F to <101.5°F	$\geq 38.6^\circ\text{C}$ to <39.3°C or $\geq 101.5^\circ\text{F}$ to <102.7°F	$\geq 39.3^\circ\text{C}$ to <40.0°C or $\geq 102.7^\circ\text{F}$ to <104.0°F	$\geq 40.0^\circ\text{C}$ or $\geq 104.0^\circ\text{F}$
Painⁱ (not associated with study intervention injections and not specified elsewhere) Specify location	Pain causing no or minimal interference with usual social & functional activities	Pain causing greater than minimal interference with usual social & functional activities	Pain causing inability to perform usual social & functional activities	Disabling pain causing inability to perform basic self care functions OR Hospitalization indicated
Serum Sickness^j	Mild signs and symptoms	Moderate signs and symptoms AND Intervention indicated (eg, antihistamines)	Severe signs and symptoms AND Higher level intervention indicated (eg, steroids or IV fluids)	Life threatening consequences (eg, requiring pressor or ventilator support)

dB: decibel; kHz: kilohertz; NAP: not applicable

PARAMETER	SYSTEMIC			
	GRADE 1 MILD	GRADE 2 MODERATE	GRADE 3 SEVERE	GRADE 4 POTENTIALLY LIFE- THREATENING
Acute Allergic Reaction	Localized urticaria (wheals) with no medical intervention indicated	Localized urticaria with intervention indicated OR Mild angioedema with no intervention indicated	Generalized urticaria OR Angioedema with intervention indicated OR Symptoms of mild bronchospasm	Acute anaphylaxis OR Life threatening bronchospasm OR Laryngeal edema
Chills	Symptoms causing no or minimal interference with usual social & functional activities	Symptoms causing greater than minimal interference with usual social & functional activities	Symptoms causing inability to perform usual social & functional activities	NAP

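### The grade 3 rash fever limit in Appendix 5 pairs 38°C with 100°F, which are different temperatures, so a mandatory permanent stop of JNJ-3989 can depend on the unit used

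*Protocol*

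**What the plan says.** Protocol Section 10.5 (Appendix 5), Table 3, lists features that raise any cutaneous event to a grade 3 rash. One of them is "Fever >38°C or 100°F". For grade 3 the action is "Must permanently discontinue JNJ-3989; no rechallenge allowed". For grade 2, treatment may go on at the investigator's discretion.

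Section 7.1 makes the table operative: among the criteria that require JNJ-3989/placebo to be stopped, it names a rash of at least "grade 3 rash (see Section 10.5, Appendix 5, Rash Management) or allergic reaction".

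Section 10.9 (Appendix 9), in the DAIDS row for non-axillary fever, sets grade 1 at "38.0°C to <38.6°C or 100.4°F to <101.5°F". Section 8.2.2 gives the route used for vital signs: "Temperature (tympanic or oral), body weight, pulse rate, and blood pressure will be assessed".

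**The concern.** A trigger for an irreversible action should be one number. Here the Fahrenheit figure is not the conversion of the Celsius figure, so two sites reading the same body temperature in different units can reach opposite conclusions. One has to stop JNJ-3989 for good; the other may continue at its discretion. The protocol also disagrees with itself, because Appendix 9 prints the right equivalent of 38.0°C.

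What is at stake is whether an individual participant loses treatment. Sample size, power and the Week 48 analysis are not involved.

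**Working it through.** **Inputs.** Table 3 limit: 38°C or 100°F (Section 10.5). DAIDS grade 1 fever: from 38.0°C or 100.4°F (Section 10.9). I read the greater-than sign in Table 3 as applying to both figures.

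**Formulas.** F = C × 9/5 + 32 and C = (F − 32) × 5/9.

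**The printed figure.** 38 × 9/5 + 32 = 100.4°F. Rounded to a whole degree this is 100°F, so rounding reproduces the Table 3 pair. Converted back, (100 − 32) × 5/9 = 37.78°C, not 38°C.

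**Check against the protocol's own table.** The DAIDS fever limits 38.0, 38.6, 39.3 and 40.0°C convert to 100.40, 101.48, 102.74 and 104.00°F. The protocol prints 100.4, 101.5, 102.7 and 104.0°F. All four agree to 0.1 degree.

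**Width of the band.** 100.4 − 100 = 0.4°F, and 0.4 × 5/9 = 0.22°C.

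| Reading (°C) | Equivalent (°F) | Above 38°C? | Above 100°F? |
|---|---|---|---|
| 37.7 | 99.86 | no | no |
| 37.8 | 100.04 | no | yes |
| 37.9 | 100.22 | no | yes |
| 38.0 | 100.40 | no | yes |
| 38.1 | 100.58 | yes | yes |

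At 0.1-degree resolution the two limits disagree on three Celsius readings (37.8 to 38.0) or four Fahrenheit readings (100.1 to 100.4). Two of the three Celsius readings, 37.8 and 37.9, are below DAIDS grade 1 fever.

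**Who was still exposed.** The Amendment 5 rationale (27 March 2024) reports that all 22 Part 1 participants had completed investigational treatment and that 17 Part 2 participants had entered the open-label phase. The ceiling is therefore 17.

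**Doses remaining.** The protocol does not give the last randomization date. Section 10.11 says only that new enrollment was halted in December 2022, so I assume a date in that month.

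- 31 December 2022 to 27 March 2024: 365 + 87 = 452 days, and 452/7 = 64.6 weeks. Doses left before end of treatment (EOT) at Week 96 (Arm 1): Weeks 68, 72, 76, 80, 84, 88 and 92, which is 7. Before EOT at Week 100 (Arm 2): the same plus Week 96, which is 8.
- 1 December 2022: 452 + 30 = 482 days, and 482/7 = 68.9 weeks. The Week 68 dose has passed, which leaves 6 (Arm 1) or 7 (Arm 2).

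No dose is counted at the EOT visit, since "At this EOT visit, JNJ-3989 will not be administered". The counts assume that Amendment 5 is in effect at the site by then. Participants randomized earlier had fewer doses left.

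**The case against.** The strongest reply is that this is whole-degree rounding and not a conflict of rules. Both figures are printed without decimals, and 100.4 rounds to 100. That explains how the slip arose. It does not remove the 0.4°F band in which the required action depends on the unit.

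A second reply is that a single answer can be found. The word between the two figures can be read as meeting either one, and the general DAIDS instructions in Section 10.9 tell sites to take the higher grade when two could apply. Those instructions belong to the DAIDS table, not to Table 3. On either reading 100°F governs and the 38°C limit does nothing, because any temperature above 38°C is already above 100°F. Readings of 37.8 and 37.9°C would then force a permanent stop although they are below grade 1 fever. That is unlikely to be intended.

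Three points stand in part:

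- Section 8.2.2 describes vital signs, and Table 3 names no route for rash visits. That the DAIDS fever row and Table 3 cover the same readings is therefore an inference. The conversion error does not depend on it.
- Section 8.3.6.2 calls for standard management "If the rash is considered to be most likely due to concomitant illness or non-study drugs", which takes some cases out. It does not say which limit holds for the rest.
- Under Section 10.3.1 a protocol change needs a formal amendment, so correcting one figure still carries that process. Few doses remained.

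A decimal lost in reading the PDF cannot be fully excluded, but the text shows no gap.

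**Conclusion.** The concern holds. Table 3 states two different limits for a mandatory, permanent stop, and the Fahrenheit figure is the wrong one if 38°C is the intended limit. The DAIDS row supports that reading, as does the fact that the Celsius figure would otherwise be idle.

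The finding is minor. It bites only in a participant with a cutaneous event, no other grade 3 feature, and a temperature inside the narrow band. Measured against 38°C it errs on the cautious side. The dose counts rest on the assumed December 2022 randomization date and only show that the rule was probably still live when Amendment 5 was issued; the conclusion does not depend on them. How many stops it could cause is unknown.

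**What to change.** In Table 3 of Section 10.5, grade 3 row, give the fever limit as >38.0°C (>100.4°F). Optionally, the opening of Section 8.3.6 could say that Table 3 governs rash management and stopping, while the DAIDS table grades the severity of adverse events.

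The edit is one figure, with no added data collection and no change to any analysis. It can go into any next amendment.
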